9.2.4 Recruitment and enrolment

[figure not shown]
Only participants who are eligible for recruitment and willing to participate in the study through written informed consent/and or assent (for children aged 13 to 17 years old) will be recruited into the study. We plan to recruit a total of 1200 participants for the SMS trial from each site. All screened people with epilepsy will be informed of the inclusion criteria and their eligibility for enrolment. Eligible participants who give consent/and or assent will then be invited for the initial study visit for enrolment into the study and baseline assessments

9.2.5. Randomisation

Participants will be randomized to four groups, with randomisation assigned via a computer-generated sequence by an independent statistician. The database manager will not know details of those SMS are being dispensed to. An allocation ratio of 1:1:1:1 across the 4 arms

will be used. A random sampling technique using computer-generated sequences will be used to ensure epilepsy factors such as focal features, age and gender are balanced between the intervention groups or arms. The SMS randomisation platform will be linked to a central database that stores a pre-generated randomization sequence, which will be generated once at the beginning of the study. Each participant will be randomized once, failure to which the system will alert the data manager and decline the request. The data manager will use an automated system to send out the messages and they will be blinded to participant details. In addition, to prevent cross-contamination due to exchange of information among participants, we will emphasise the need to keep allocation among confidential the participants and schedule follow up visits for participants in different arms on different days. However, cross-contamination may still occur in the community, and this will be considered during interpretation of the findings.

Figure 1. Recruitment strategy and randomization

*All people with epilepsy in the databases will be screened for eligibility

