In this study, we plan to test the use of short message service (SMS) reminders sent to remind people with epilepsy to take their medication as prescribed and to engage the Kilifi and Nairobi County Departments of Health to ensure a continuous supply of medications used to manage epilepsy. A previous audit at the epilepsy clinic in Kilifi showed that about 90% of people with epilepsy, either through direct ownership or via a caregiver or a member of the household, have access to basic mobile phones that can receive unique text or graphic messages. After rolling out the SMS reminders, we will compare the different modes of messaging (graphic versus text) to find out which is more acceptable and successful in our local setting.

Where is the study taking place, how many people does it involve and how are they selected?

This study will take place in Kilifi and Nairobi Counties, within two defined areas known as the Kilifi Health and Demographic Surveillance System (KHDSS) and the Nairobi Urban Health and Demographic Surveillance System (NUHDSS). In Nairobi, we will also conduct the study within clinics led by the Kenya Association for the Welfare of People with Epilepsy (KAWE). Before the roll out of the intervention, we will hold about 3 pre-study focus group discussion with about 10 PWE and one of their family members each about the preferred nature of SMS reminders and the timing and frequency. We plan to include 1,200 people with epilepsy (PWE) from each site. In Kilifi, PWE will be randomly selected from a large database of patients attending the Neuroscience epilepsy clinic, of whom majority were identified from previous large-scale community surveys within the KHDSS. In Nairobi, PWE will be randomly selected from those identified through a survey conducted by the African Population and Health Research Center (APHRC) within the NUHDSS and patients attending KAWE-led clinics. At each site, we will randomly divide the participants into four groups of 300 people with epilepsy, to receive either text SMS, graphic SMS, both text and graphic or no intervention/non-reminder SMS (for comparison). Participants will be screened for eligibility by the attending epilepsy clinicians and referred to the field assistant for consenting and/or assenting and recruitment into the study.

What does the study involve for those who are in it?

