8.5 Intervention Compliance

It will be possible to view a delivery report of whether the messages were received or not due to network issues. After the screening visit, all participants will be contacted via phone call to check that their phones can receive the messages. Prior to the commencement of the SMS trial, ongoing EPInA studies will conduct engagements with the respective county departments of health on sustained availability of ASM at the health facilities within the study area where PWE are likely to visit for medication refill. Primarily PWE will visit the study clinics (epilepsy clinic in Kilifi, two APHRC clinics in Nairobi and one KAWE-led clinic in Nairobi). However, due to ongoing capacity building and task sharing studies in Kilifi (the mhGAP study), some PWE may visit any of the 128 public peripheral health facilities already contributing primary health care providers for training. Since adherence may also be affected by availability of medications, we hope to be able to lobby for the set-up of an SMS platform to monitor supply and re-ordering of ASMs in Kilifi and Nairobi County in addition to ongoing engagements with the counties as part of capacity building and task sharing within the EPInA studies.

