12.0 STATISTICS

12.1 Determination of sample size

The minimum sample size determination will be based on reducing the adherence treatment gap from the current estimates of 62% in Kilifi ((Ibinda et al., 2017a) aiming for a proportion of improvement of 40%-50%. Previous studies have shown non-adherence of >60% even among clinic attendants, especially when symptoms subside. Assuming a refusal/non-consent/attrition rate of 10% and design effect of 1.5 (assuming possibility of modest clustering), if we recruit 300 patients at each arm, i.e., total of 1200 patients, we will have 95% power to detect a 50% improvement in adherence. Therefore 1,200 PWE will be randomized into 4 arms as follows: text SMS (N=300), graphic SMS (N=300), both text and graphic SMS (N=300) and control/non-reminder SMS (N=300). An allocation ratio of 1:1:1:1 across the 4 arms will be used. Since no prevalence estimates exist for the Nairobi site, we will utilise a similar sample size for each site. This sample size determination will account for these unprecedented withdrawals by recruiting a surplus of participants, assuming a proportion of 20% loss to follow up.

Table 2. Sample size adjusted for 10% attrition at varying improvements and powers

Improvement	Power			
	80%	90%	95%	
40%	588	786	971	
45%	268	358	442	
50%	154	205	253	

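### Section 9.2.5 promises balance on focal features, age and gender but names no allocation method that delivers it, and section 12.2 names no adjustment for these factors, site or clinic

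*Combined protocol and SAP*

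**What the plan says.** Section 9.2.5 sets "An allocation ratio of 1:1:1:1 across the 4 arms" and states the aim of restricting the allocation: "A random sampling technique using computer-generated sequences will be used" in order "to ensure epilepsy factors such as focal features, age and gender are balanced between the intervention groups or arms". The mechanism it describes is a central database that "stores a pre-generated randomization sequence, which will be generated once at the beginning of the study". It gives no strata, block size, minimisation rule or cut-point for age, and it does not mention site or clinic.

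Other sections set targets by site. Section 9.2.4: "We plan to recruit a total of 1200 participants for the SMS trial from each site". The lay summary (2.0): "At each site, we will randomly divide the participants into four groups of 300 people with epilepsy". Section 12.1 builds its power claim on the same numbers ("Therefore 1,200 PWE will be randomized into 4 arms as follows", 300 in each) and applies them to both sites. Section 8.5 lists the study clinics: "epilepsy clinic in Kilifi, two APHRC clinics in Nairobi and one KAWE-led clinic in Nairobi".

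Sections 12.2.1 and 12.2.2 compare adherence between arms with binomial, log-link GEE and GLM. Neither names site, clinic, age, sex or focal features as a covariate in those comparisons.

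**The concern.** The plan guarantees a property of the allocation without stating a method that produces it. A statistician could not build the list from section 9.2.5. If the list were unrestricted, the named factors would be balanced only in expectation, and 300 per arm per site would be a target and not a result.

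Clinic is the notable omission. Participants come from a long-standing clinic database in Kilifi, from survey-found cases seen at two clinics in Nairobi informal settlements, and from one KAWE-led clinic. Section 8.5 accepts that drug availability may affect adherence, and section 12.1 allows for modest clustering through a design effect of 1.5. Age plausibly affects who reads and acts on a message. If neither the allocation nor the model uses these factors, chance differences on them add noise to every arm contrast, including text against graphic, and an observed imbalance would prompt unplanned adjustment after the fact.

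**Working it through.** **Inputs.** 1,200 per site, four arms, 1:1:1:1 (9.2.4, 9.2.5); 300 per arm per site (2.0, 12.1); non-adherence 62%, attrition 10%, design effect 1.5, 95% power for a 50% improvement (12.1). Assumed, because the documents do not say: simple randomisation, factor prevalences, independence of the three factors, and two-sided alpha of 0.05.

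**1. The plan's own figure.** Adherence is 1 − 0.62 = 0.38, and a 50% relative improvement gives 0.57. Effective n per arm = 300 × 0.9 / 1.5 = 180. With mean proportion 0.475:
- null SE = √(0.475 × 0.525 × 2/180) = 0.0526
- alternative SE = √((0.38 × 0.62 + 0.57 × 0.43)/180) = 0.0517
- power = Φ[(0.19 − 1.96 × 0.0526)/0.0517] = Φ(1.68) = 95.4%

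The stated 95% reproduces, so 300 per arm per site is the number on which the claim rests.

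**2. Arm sizes under simple randomisation.** SD = √(1200 × 0.25 × 0.75) = 15.0. The 95% range is about 271 to 329. By simulation, some arm is off by 20 or more in 51% of runs. A single list fixed at 600 per arm over both sites, without site strata, would still leave an SD of 10.6 per arm per site (279 to 321).

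**3. What uneven arms cost.** Replace 300 v 300 by 270 v 330, using the formula in step 1 with separate arm sizes.
- 0.38 v 0.57 (effective 162 and 198): power goes from 95.4% to 95.2%.
- 0.30 v 0.45 (sizes divided by 1.5 × 1.1): from 84.3% to 83.8%.

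The loss is under 1 point.

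**4. Factor balance at 300 per arm.** For one factor and one pair of arms, the SD of the difference is √(2p(1 − p)/300). At p = 0.5 this is 0.0408, so the 95% limit is 1.96 × 0.0408 = 8.0 points; at p = 0.2 it is 0.0327, so 6.4 points. For a single contrast on a single factor at p = 0.5, a difference of more than 8 points has probability about 0.045.

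With three factors and three reminder arms there are nine comparisons with control. I simulated Binomial(300, p) counts and took *more than 8 points* as more than 24 people and *more than 10 points* as more than 30:

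| Prevalence of each factor | Some gap > 8 points | Some gap > 10 points |
|---|---|---|
| 20% | 0.10 | 0.02 |
| 35% | 0.25 | 0.07 |
| 50% | about 0.30 | about 0.10 |

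Letting arm sizes vary as in step 2 moves the last row to 0.33 and 0.11. With both sites pooled (600 per arm, 50% prevalence), the figures fall to about 0.04 and 0.004.

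**5. What a restricted method gives.** As an illustration, take eight strata per site (focal features × two age groups × gender, equal expected sizes, assumed) in permuted blocks of 8. Arms stay at about 296 to 304, and the mean largest gap on a stratified factor is 0.6 points. Blocking by site alone gives exactly 300 per arm at 1,200 but does nothing for the three factors.

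**The case against.** A reader might infer that the trial will use one unstratified, unblocked list. The documents do not say that. They are silent: a sequence generated once at the start can be stratified and blocked, section 9.2.5 uses the plural *sequences* once, and Figure 1, on recruitment and randomisation, is not reproduced in the text available here. Nor does advance generation mean that participants' characteristics come too late to use. Table 1 places demography and medical history at screening, before the randomisation visit, so an allocation could be drawn from the right stratum.

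A reader might also infer that site is ignored. The lay summary intends division within each site, and Kilifi has one study clinic, so within-site allocation would deal with clinic there. The remaining gap is the three Nairobi clinics, plus the fact that section 9.2.5 does not carry the within-site intention.

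Finally, chance imbalance does not bias a randomised comparison; its variability is already in the standard error. The 0.30 pools nine comparisons, rests on assumed prevalences, and drops sharply if the sites are pooled.

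All of this stands and limits the point. It does not supply the missing method, and it does not support the word *ensure*.

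**Conclusion.** The point holds as a gap in specification with a modest statistical cost. Section 9.2.5 guarantees balance on three factors and states no method that gives it, and section 12.2 has no planned adjustment to fall back on. If allocation were simple, arm size would have an SD of 15 per site. A gap of more than 8 points between some reminder arm and control on at least one of three factors would occur with probability about 0.30 per site at 50% prevalence (0.10 at 20%), and a gap of more than 10 points with probability about 0.10 (0.02 at 20%). Simple randomisation, the prevalences and independence are assumptions.

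The documents do not support a claim that the arm comparisons would be biased or the trial underpowered for this reason: uneven arms cost under 1 point of power. What is at stake is precision, a prespecified treatment of known prognostic factors, and a guarantee that nothing written supports. It should be changed before the sequence is generated, because it is generated only once.

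**What to change.** **Section 9.2.5.** State that allocation uses separate pre-generated lists in randomly permuted blocks within each site, stratified by clinic (Kilifi, Korogocho, Viwandani, KAWE) and age group (under 18 v 18 and over), held on the same central platform with block sizes concealed from clinic staff. That is 4 × 2 = 8 lists. With blocks of 4 and 8, an incomplete block leaves any two arms at most 2 apart, so the largest possible gap is 2 × 2 = 4 in Kilifi (two lists) and 6 × 2 = 12 in Nairobi (six lists). Gender and focal features are not strata here, so replace *ensure* for them with wording that balance is expected on average and handled in the analysis. If the sponsor wants to keep the guarantee for them, they must become strata as well.

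**Section 12.2.** Include clinic, age, sex and focal features as prespecified baseline covariates in the adherence GEE and GLM. This also keeps the analysis in line with the stratified allocation. Log-binomial models with added covariates may not converge, so name a fallback, such as modified Poisson regression with robust standard errors.

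**Cost.** A few more lists, a platform that asks for clinic and age before releasing an allocation, and slightly more analysis work. Clinic is known at recruitment, demography is taken at screening and seizure semiology at baseline, so there is no added burden on participants.

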9.2.6. Procedures

(i) Clinical evaluation, assessment of stigma scores and measures of quality of life

During the baseline visit, information regarding epilepsy factors including seizure semiology, electroencephalography (EEG) and medical co-morbidities as well as sociodemographic characteristic will be assessed using tools that have been validated in this setting. Comprehensive clinical examination, and assessment of self-reported sigma and measures of quality of life and collection of blood samples will also be conducted at the baseline visit. Stigma scores will be assessed using standardized Kilifi Epilepsy Stigma Scale and while quality of life will be assessed using the World Health Organization Quality of Life Scale (WHOQOL-BREF). These tools will be validated for the Nairobi site prior to administration.

(ii) Measurement of adherence

Information on adherence to ASMs will also be collected using a validated self-reporting tool, the Morisky Medication Adherence Scale (MMAS-8) and validated using blood samples. Blood will be drawn (not exceeding 5mls) to measure detectable and optimal plasma levels of ASMs at baseline and during three follow up timepoints; at three months, six months and at 12 months (table 1). Optimal and detectable levels of ASMs in blood. All assays for ASMs will be done at the end of the study using a TDxFx analyser and automated VitaLab Selectra E Clinical Chemistry (Abbott Laboratories, Abbott Park, IL, USA) at Centre for Research in Therapeutic Sciences (CREATEs), Strathmore University.

(iii) Short message service (SMS) intervention

An automated computer system will be used to generate standard text messages to remind patients to take their ASMs at the prescribed time and to refill their prescriptions. The system will have an algorithm to check time, send the text message and generate a delivery report. Participants will be able to send replies to the messages, either via text or USSD codes at no cost. A three-step verification SMS system will be designed to send a delivery report (which shows if the message has been delivered) and a read receipt (which shows if the message has been opened) back to the service provider and study team and each message will prompt for a USSD or text response at no cost to the participant asking if they have read the message. The participants in the no-intervention group will receive routine care, including clinic appointment for review of symptoms and medication review and refills and routine electroencephalography (EEG) recordings. For comparability, the control group will receive

public health promotion messages (not related to epilepsy) such as use of bednets. All other data will be collected in the case report forms during scheduled follow up visits at the clinic.

(iv) Anti-seizure medication (ASM)-related adverse drug reactions (ADRs)

Cognisant that this trial doesn't involve administration of medicinal products, we would like to document and describe reported drug-related adverse events of ASM as part of routine care. These data have not been previously systematically documented in relation ASM use in the study population. ASM-related adverse drug reactions will be documented and graded according to Common Toxicity Criteria for Adverse Events (CTCAE), including date and time of onset, severity, and relationship to drug administration. Standardised assessment will be used to measure various emerging ADRs. These data will be used in a secondary analysis to investigate the association of toxicity with ASM concentrations. Any side effects of ASMs will be documented for all the participants and correlated with type of ASM used and where possible, the ASM levels in blood. This will include abnormalities during pregnancy such as congenital abnormalities/birth defects since certain ASMs such as sodium valproate are known to be teratogenic. This information will be collected into case review forms at baseline and during follow up visits.

9.3 Follow-up Visit(s) and End of Treatment Visit

Participants will be invited to the study clinics for follow up visits to examine adherence to anti-seizure medications and assess their quality of life and stigma scores three, six and twelve months from the first visit. The long follow up period per individual of 12 months is selected to ensure high exposure to the intervention to show proof of concept. All other routine clinical assessments will be done during this follow up visit including physical examination, EEG recordings and medication refill. Participants who fail to show up for scheduled follow up visits will be contacted by telephone up to three times and if unsuccessful, followed up at home to remind them to come for their scheduled visits. Participants who are not reached after 3 telephone calls and one home visit will be considered lost to follow up.

Table 1: Study Schedule

	Screening visit 1	Pre-enrolment screening call	Randomisation visit 2 at baseline	Follow up visits 1	Follow up visits 2	End of intervention
Study Month	Use available data	-1 week	0	3	6	12
Assessment / Procedure						
Provide Patient Information Sheet and Informed Consent Form and/or Assent Form	x					
Obtain written informed consent and/or assent	x					
Call to check phone availability/accessibility		x				
Demography	x					
Medical history	x					
Physical examination	x		x	x	x	x
Vital statistics e.g., heart rate and blood pressure	x		x	x	x	x
12-lead EEG	x					x
Blood for adherence levels	x		x	x	x	x
Morisky self-reported scale	x		x	x	x	x
Stigma scores scale	x		x	x	x	x
Quality of life scale			x	x	x	x

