13.3 Withdrawal of Study Participants

Participant may opt to withdraw from the study at any point. The study team may withdraw them from the study if it is established that they are not accessing SMS, have missed two of the follow up periods, have stopped taking anti-seizure medications following advice by the attending clinician or those who have emigrated or died. Participants may terminate their participation prematurely, or have their participation terminated by the Investigator

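### Section 13.3 lets the team withdraw someone who missed months 3 and 6 before the month-12 outcome visit, and 9.3 does not say whether lost to follow up is final

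*Combined protocol and SAP*

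**What the plan says.** Two parts of the protocol deal with participants who stop attending.

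- **Section 9.3 (Follow-up Visit(s) and End of Treatment Visit)** starts from non-attendance: "Participants who fail to show up for scheduled follow up visits will be contacted by telephone up to three times". A home visit follows if the calls fail. Then: "Participants who are not reached after 3 telephone calls and one home visit will be considered lost to follow up". No minimum number of missed visits is set, so the status can be given at month 3.
- **Section 13.3 (Withdrawal of Study Participants)** gives the team discretion to withdraw participants who "have missed two of the follow up periods". Other grounds stand beside it: not accessing the SMS, stopping medication on clinician advice, emigration and death. They are not part of this point.

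Neither section refers to the other. Neither says whether a participant lost at one visit is invited to the next.

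Section 9.2.6 and Table 1 place the blood sample and the MMAS-8 at baseline and at months 3, 6 and 12. Section 12.2.2 plans generalised estimating equations (GEE) across those four time points and log-binomial models at each one, in FAS, ITT and per-protocol sets. It gives no method for missing data.

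**The concern.** In an ITT comparison, outcomes should be sought from everyone randomised, whether or not they kept earlier appointments. Section 13.3 makes attendance a reason to leave the study. Someone who misses months 3 and 6 has no post-baseline blood level or MMAS-8 except a possible one at month 12, so withdrawal before then removes their only follow-up outcome.

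Those affected are unlikely to be a random subset. Section 9.3 makes medication refill part of the follow-up visit, so missed visits plausibly go with poor adherence. The reminder messages prompt refills (synopsis 1.4 and section 9.2.6), so attendance may also differ by arm. Unweighted GEE does not correct for dropout that depends on unobserved adherence, and uncollected data cannot be restored in the analysis.

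Temporary loss of contact is foreseeable. Section 5.1 reports that 44 of 222 people in a Kilifi clinic audit owned a phone, and section 5.2 expects changed numbers, changed handsets and network disruption.

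**Working it through.** **1. The two rules side by side**

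| | 9.3 | 13.3 |
|---|---|---|
| Trigger | visit missed and person not reached by calls and home visit | visits missed, reached or not |
| Missed visits needed | one | two |
| Force | status is assigned | team may act |
| Stated result | considered lost to follow up | withdrawn from the study |
| Later visits | not stated | ended by withdrawal |

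With three follow-up visits there are three ways to miss exactly two: months 3 and 6, 3 and 12, or 6 and 12. Only the first leaves a visit that withdrawal can cancel, and that visit is month 12.

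**2. The plan's own power figure**

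Section 12.1 rests on "reducing the adherence treatment gap from the current estimates of 62% in Kilifi", that is, 38% adherent. It uses 300 per arm, 95% power for a 50% improvement, and this: "Assuming a refusal/non-consent/attrition rate of 10% and design effect of 1.5". No alpha is stated; two-sided 5% is assumed. Reading the improvement as relative, 38% x 1.5 = 57%. Effective n = 300 x 0.9 / 1.5 = 180 per arm. Power for 38% against 57% is 95.4%, which reproduces the stated 95%. That figure does not depend on the attendance rule.

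**3. Completeness at month 12 (illustration)**

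Assume a rate q of missing a visit, equal and independent across visits, with every missed visit also unreached. Month-12 data are present with probability:

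- A, first unreached miss is final: (1 - q)^3
- B, only missing both months 3 and 6 ends follow-up: (1 - q^2)(1 - q)
- C, everyone is sought at every visit: 1 - q

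Power is for 38% against 57% with effective n = 300 x completeness / 1.5. Each cell shows completeness, then power.

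| q | A | B | C |
|---|---|---|---|
| 5% | 85.7%, 94.4% | 94.8%, 96.2% | 95.0%, 96.3% |
| 10% | 72.9%, 90.5% | 89.1%, 95.2% | 90.0%, 95.4% |
| 15% | 61.4%, 85.1% | 83.1%, 93.8% | 85.0%, 94.3% |
| 20% | 51.2%, 78.1% | 76.8%, 91.9% | 80.0%, 92.9% |

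The 13.3 rule alone costs C - B = q^2(1 - q): 0.9 points at q = 10% (300 x 0.009 = 2.7 people per arm) and 3.2 points at q = 20% (9.6 per arm). Real misses tend to cluster in the same people. More would then miss both early visits, though fewer of those would attend at month 12.

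Reading A matters more. Loss reaches 10% at q = 1 - 0.9^(1/3) = 3.45%, and 20% at q = 1 - 0.8^(1/3) = 7.17%. The 20% is the other allowance in 12.1: "assuming a proportion of 20% loss to follow up".

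**4. Bias under no true effect (illustration, all rates assumed)**

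Let 85% of each arm attend reliably with 45% adherence, and 15% attend poorly with 20% adherence. Follow-up is closed early for all the poor attenders in control (15% of the arm) and for 8% of the reminder arm.

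- True adherence, both arms: 0.85 x 0.45 + 0.15 x 0.20 = 0.4125
- Observed, control: 0.450
- Observed, reminder: (0.85 x 0.45 + 0.07 x 0.20) / 0.92 = 0.3965 / 0.92 = 0.431
- Observed RR: 0.431 / 0.450 = 0.958, a false difference of 1.9 points

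Range with the same adherence values: equal closure gives RR 1.00; no closure in the reminder arm gives 0.4125 / 0.45 = 0.917. If closure were heavier in the reminder arm, the ratios invert to 1.04 and 1.09. The direction is therefore not fixed.

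**The case against.** The strongest reply is that the text is mostly silent rather than wrong. Several stronger readings are tempting, and the documents do not support them.

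- **A reader might infer that 9.3 and 13.3 contradict each other.** They do not. One classifies people who cannot be reached; the other is an optional rule on attendance. A person who misses only month 3 and is then reached falls under neither.
- **A reader might infer that a site must stop inviting anyone labelled lost.** Section 9.3 does not say so. Reading A in the working is one reading of a silent text, not a stated rule.
- **A reader might infer that a switched-off phone is enough to lose someone.** A home visit follows the failed calls, and participants also remain in routine care.
- **A reader might infer that the two sites will apply different rules.** One protocol covers both, and nothing in it sets separate rules.
- **A reader might treat the whole 20% loss allowance (240 of 1,200 per site) as recoverable early closures.** It is an overall allowance and includes people first lost at month 12. The bias scenario closes far fewer: 15% of 300 plus 8% of 900 = 45 + 72 = 117 per site.

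It can also be said that month 12 is nowhere named as the primary time point, and that GEE uses earlier visits. That is fair for someone lost after month 3 has been measured. It does not help for someone who missed both months 3 and 6, who has no earlier follow-up outcome to contribute.

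The small cost of 13.3 under independent misses, and the fact that every rate in the bias example is assumed, also stand. They limit the size claimed. They do not remove the permission to withdraw on attendance.

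**Conclusion.** The point holds as a cheap improvement. Section 13.3 expressly permits withdrawal of a randomised participant after two missed follow-up periods, which can cancel the month-12 measurement of someone still willing to attend. Section 9.3 leaves open whether lost-to-follow-up status is final and how it relates to 13.3.

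The size is unknown. At an assumed 10% miss rate per visit, independent across visits, month-12 completeness is 89.1% under the two-miss rule against 90.0% with continued follow-up. It would fall to 72.9% only if the first unreached miss were treated as final. The bias example gives an RR of about 0.96 under no true effect; it assumes that poor attenders adhere less and that closure differs by arm. That 1.9-point distortion is small beside the 19-point difference (38% to 57%) that reproduces the planned power. No figure stated in the plan is shown to be wrong.

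**What to change.** 1. In 13.3, remove two missed follow-up periods as a ground for ending outcome collection.
2. In 9.3, state that a visit at which the participant cannot be reached is recorded as a missed visit, and that every randomised participant who has not withdrawn consent or died is invited and traced again at each remaining visit, always including month 12.
3. Keep any lost-to-follow-up label as a status for reporting, separate from the decision to seek outcomes. Whether it is assigned per visit or only after month 12 is a matter of convention.

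The cost is protocol wording plus repeat calls and home visits. Section 19.2 already budgets four fieldworkers whose duties include household visits. At an assumed 10% unreached at month 3, about 120 of 1,200 participants per site would be kept on the invitation list for month 6. The downside is small: some tracing effort will yield nothing.
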